#### **15.2.4.2.Biochemical toxicities**

The following units for SGOT/SGPT, bilirubin, alkaline phosphatase and creatinine will be used for the analysis of biochemical toxicity :

Parameters	Units
SGOT/SGPT	IU/l
Bilirubin	µmol/l
Alkaline phosphatase	IU/l
Creatinine	µmol/l

If values were expressed in different units in the CRF, the data management department will be in charge of the conversion to SI units.

Calculation of grades will be done using the following boundaries :

Grade	SGOT/SGPT	Bilirubin	Alkaline phosphate	Creatinine
Grade 0	[LLN – UNL]	[LLN – UNL]	[LLN – UNL]	[LLN – UNL]
Grade 1	]UNL – 2.5 x UNL]	]UNL – 1.5 x UNL]	]UNL – 2.5 x UNL]	]UNL – 1.5 x UNL]
Grade 2	]2.5 – 5 x UNL]	]1.5 – 3 x UNL]	]2.5 – 5 x UNL]	]1.5 – 3 x UNL]
Grade 3	]5 – 20 x UNL]	]3 – 10 x UNL]	]5 – 20 x UNL]	]3 – 6 x UNL]
Grade 4	> 20 x UNL	> 10 x UNL	> 20 x UNL	> 6 x UNL

Of note, the study data manager calculates grades of biochemical toxicities before database is made available to the study statistician on a read-only basis.

#### ***15.2.4.3. Definition of a toxic death***

A toxic death is defined as a death caused by a related adverse event either during the treatment period or in the 30 days following the last administration.

#### ***15.2.4.4. Treatment duration***

For arm A, the treatment duration is defined as the time elapsed between the date of 1st administration and the date of the last VFL administration (if MTX not given) + 21 days or the date of the last MTX administration (if given) + 14 days. For arm B, the treatment duration is defined as the time elapsed between the date of the 1st administration and the date of the last D1 administration of the last cycle + 21 days (if D8 and D15 not given) or the date of the last D8 administration of the last cycle + 14 days (if D15 not given) or the date of the last D15 administration of the last cycle + 7 days (if D15 given). Treatment duration will be tabulated by treatment arm, and listed by patient.

### **15.2.5. End of study**

#### ***15.2.5.1. Death for progression***

In case of death for progression (so PD documented in the tumour assessment form and death documented in death report form are at the same date), the reason for treatment discontinuation is **Progression**.

### 15.3. APPENDIX 3: ADVERSE EVENTS OF SPECIAL INTEREST

Adverse Events of Special Interest		MedDRA (v19.0) Preferred Terms (PT) or High Level Terms (HLT) if specified or graded from laboratory values if specified
1	Myelosuppression	neutropenia, leukopenia, anaemia, thrombocytopenia to be graded from haematological lab values
2,1	Febrile Neutropenia	
	PT	febrile neutropenia
2,2	Infections with severe neutropenia (Clinically relevant Infections (potential bacterial origin))	Time window is defined as 2 days before through 1 day after the onset of an infection during which time grade 3 or 4 neutropenia or grade 4 leukopenia coincides.
	PT	neutropenic infection
	PT	neutropenic sepsis
	PT	abscess limb
	PT	bacteraemia
	PT	bacterial infection
	PT	blood culture positive
	PT	bronchitis bacterial
	PT	cellulitis
	PT	cystitis
	PT	ear infection
	PT	febrile infection
	PT	fungal infection
	PT	gastrointestinal infection
	PT	infection
	PT	lobar pneumonia
	PT	localised infection
	PT	lower respiratory tract infection bacterial
	PT	lower respiratory tract infection
	PT	lung infection
	PT	oral infection
	PT	pneumonia
	PT	pneumonia bacterial
	PT	sepsis

	PT	septic shock
	PT	sinusitis
	PT	sinusitis bacterial
	PT	skin infection
	PT	tooth abscess
	PT	tooth infection
	PT	urinary tract infection
	PT	urosepsis
	PT	catheter related infection
	PT	wound infection
3,1	Constipation	
	PT	constipation
3,2	Ileus	
	PT	ileus paralytic
	PT	ileus spastic
	PT	ileus
	PT	subileus
	PT	megacolon
3,3	Intestinal Obstruction	
	PT	gastrointestinal obstruction
	PT	intestinal obstruction
	PT	small intestinal obstruction
	PT	large intestinal obstruction
	PT	mechanical ileus
	PT	colonic obstruction
	PT	gastrointestinal stenosis
	PT	intestinal stenosis
	PT	colonic stenosis
3,4	Abdominal Pain	
	PT	Abdominal pain
	PT	Abdominal pain lower
	PT	abdominal pain upper
	PT	abdominal rebound tenderness

	PT	abdominal tenderness
	PT	gastrointestinal pain
	PT	visceral pain
4,1	Nausea	
	PT	Nausea
4,2	Vomiting	
	PT	Vomiting
4,3	Stomatitis/mucositis	
	PT	aphthous stomatitis
	PT	mouth ulceration
	PT	mucocutaneous ulceration
	PT	mucosal inflammation
	PT	mucosal ulceration
	PT	stomatitis
	PT	stomatitis haemorrhagic
4,4	Diarrhoea	
	PT	Diarrhoea
5,1	Myocardial Infarction/ Ischaemia	
	PT	acute myocardial infarction
	PT	myocardial infarction
	PT	silent myocardial infarction
	PT	papillary muscle infarction
	PT	acute coronary syndrome
	PT	angina pectoris
	PT	angina unstable
	PT	Prinzmetal angina
	PT	myocardial ischaemia
	PT	ECG signs of myocardial ischaemia
5,2	Cardiac Arrhythmias	
	HLT	Rate and rhythm disorders NEC
	HLT	supraventricular arrhythmias
	HLT	Ventricular arrhythmias and cardiac arrest
5,3	Cardiac Conduction Disorders	

	HLT	Cardiac Conduction disorders
6,1	Local Injection/Infusion Site Reactions	
	HLT	injection and infusion site reactions (minus Infusion Site Extravasation and Injection Site Extravasation)
6,2	Extravasation	
	PT	Extravasation
	PT	Infusion site extravasation
	PT	Injection site extravasation
7,1	Peripheral Sensory Neuropathy	
	PT	Acute polyneuropathy
	PT	Burning sensation
	PT	Dysaesthesia
	PT	Hyperaesthesia
	PT	Hypoesthesia
	PT	Neuritis
	PT	Neuropathy Peripheral
	PT	Allodynia
	PT	Pallanaesthesia
	PT	Paraesthesia
	PT	Peripheral sensory neuropathy
	PT	Polyneuropathy
	PT	Toxic neuropathy
7,2	Peripheral Motor Neuropathy	
	PT	Neuromuscular toxicity
	PT	Peripheral motor neuropathy
	PT	Peripheral sensorimotor neuropathy
7,3	Autonomic Neuropathy	
	PT	autonomic neuropathy
	PT	cardiac autonomic neuropathy
	PT	neurogenic bowel
	PT	impaired gastric emptying
8,1	Asthenia/fatigue	
	PT	fatigue

	PT	asthenia
8,2	Myalgia	
	PT	Myalgia
9	Immediate Hypersensitivity	events must be study drug related and occur on the day of study drug infusion (day 1 or within 24 hours after infusion of vinflunine)
	PT	Allergic oedema
	PT	Anaphylactic reaction
	PT	Anaphylactic shock
	PT	Anaphylactoid reaction
	PT	Anaphylactoid shock
	PT	Angioedema
	PT	Bronchospasm
	PT	Bronchial oedema
	PT	Circulatory collapse
	PT	Circumoral oedema
	PT	Drug hypersensitivity
	PT	Drug eruption
	PT	Epiglottic oedema
	PT	Eyelid oedema
	PT	Face oedema
	PT	Flushing
	PT	Hypersensitivity
	PT	Laryngeal oedema
	PT	Laryngospasm
	PT	Laryngotracheal oedema
	PT	Lip swelling
	PT	Lip oedema
	PT	Pharyngeal oedema
	PT	Pruritus generalised
	PT	Rash pruritic
	PT	Shock
	PT	Type I hypersensitivity
	PT	Urticaria

10	SIADH	
	PT	Inappropriate antidiuretic hormone secretion
	PT	blood antidiuretic hormone increased
11	PRES	
	HLT	Encephalopathy NOS
12	Hepatic dysfunction	use total bilirubin of grade >2 combined with either AST grade >2, ALT grade >2 or alkaline phosphatase grade >2

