4.2. EXCLUSION CRITERIA

If any of the following apply, the patient must not enter into the study:

1. Nasopharyngeal carcinoma
2. History of brain or leptomeningeal involvement
3. History of other cancers except other synchronous head and neck squamous cell carcinomas, adequately treated in situ carcinoma of the cervix uteri, basal or squamous cell carcinoma of the skin or other cancer curatively treated with surgery and/or radiotherapy (with or without other anti-cancer therapy) and with no evidence of disease for at least 3 years
4. Albumin level < 35 g/L
5. Patients with weight loss \geq 5% within the last 3 months

6. Recurrent pulmonary or upper airways infections (3 times or more in the last 3 months) requiring antibiotics and/or any infection requiring antibiotics within the last month before study entry
7. Grade ≥ 2 peripheral neuropathy at study entry according to NCI-CTC AE (version 3.0)
8. Serum potassium < the lower limit of normal
9. ECG demonstrating a QT/QTc interval > 480 msec
10. A female is not eligible to enter the study if :
 - . Pregnant or lactating
 - . With positive pregnancy test at inclusion
11. Female of childbearing potential who is unwilling or unable to use a medically accepted method to avoid pregnancy during the 2 months preceding the start of study treatment, throughout the study period and at least 3 months following the last dose of study treatment
Male unwilling or unable to use a medically accepted method to avoid pregnancy throughout the study period and at least 3 months following the last dose of study treatment if their partners are women of childbearing potential
12. Patients with any underlying medical condition that might be aggravated by treatment or which cannot be controlled i.e. active serious infection, poorly controlled diabetes mellitus, concurrent heart failure [New York Heart Association (NYHA) class III-IV] or with progressive or unstable angina, myocardial infarction within 6 months, and/or poorly controlled hypertension.
13. "Third space" fluids (pleural effusion, ascites, massive edema)
14. Concomitant treatment with any other anti-cancer therapy and contraindicated medication (see Section 6.1)
15. Prior treatment with vinca-alkaloids and methotrexate
16. Participation into a clinical study of an investigational agent within 30 days before study entry

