5.2.2.2. Treatment modifications for haematological toxicity

Complete blood cell counts will be performed on days 1 and 8 of each cycle during the treatment period. If a patient experienced fever (temperature $\geq 38^{\circ}\text{C}$) and/or developed infection, blood cell count should be immediately performed.

Cycle delay

Cycle is considered delayed if Day 1 treatment has been performed:

- either $\geq 21 + 4$ days since last Day 1 study drug administration (i.e., Day 26 or more).
- or $\geq 14 + 4$ days since last Day 8 study drug administration

Neutrophil count should be $\geq 1.5 \times 10^9/\text{L}$ (grade 1) and platelet count $\geq 100 \times 10^9/\text{L}$ before each new cycle.

Table 5 details haematological toxicity which must result in cycle delay.

Table 5: Dose delay for haematological toxicity on day 1 of each cycle

Haematological toxicity on scheduled day 1			Day 1 administration of study treatment
Absolute neutrophils		Platelets	
$\text{ANC} \geq 1.5 \times 10^9/\text{L}$	And	$\geq 100 \times 10^9/\text{L}$	No dose modification. Treat on time
$\text{ANC} < 1.5 \times 10^9/\text{L}$	And/Or	$< 100 \times 10^9/\text{L}$	Delay one week and reassess

If recovery has not occurred after a 2-week delay, the treatment will be discontinued unless approved by the sponsor.

Dose modifications

Table 6 details haematological toxicity which must result in dose reduction.

Table 6: Dose modifications for haematological toxicity

Haematological toxicity during the previous cycle	Dose adjustment for next cycle
---	--------------------------------

Grade 3 thrombocytopenia (platelets $\geq 25 \times 10^9/L$ and $< 50 \times 10^9/L$) with significant bleeding or requiring transfusion	
First appearance : decrease one dose level
 
Second appearance : decrease one dose level
 
Third appearance : stop treatment

Grade 4 thrombocytopenia (platelets $< 25 \times 10^9/L$)	
Grade 4 neutropenia (ANC $< 0.5 \times 10^9/L$) lasting ≥ 5 days	
Neutropenic infection (grade ≥ 3 neutropenia concomitant with grade ≥ 3 infection)	
Febrile neutropenia of any grade	

5.2.2.3. *Treatment modifications for non-haematological toxicity*

Based on prior clinical experience of i.v. vinflunine, non-haematological adverse events which may require treatment modification include :

- nausea and vomiting
- constipation
- stomatitis
- and peripheral neuropathy.

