11.5.6.2. Efficacy and Safety Interim Analysis

An interim analysis based on the non progression rate at 6 weeks will be performed after tumour response data from the first 100 randomised patients in the test arm become available. The main purpose of this interim analysis is to stop the study if result indicating poor efficacy of the test regimen is observed. It is assumed that the test arm will be of no further interest in the second-line treatment of SCCHN patients if the observed non-progression rate at 6 weeks (first tumour assessment scheduled) is less than the lower limit of the 95% CI of the expected non-progression rate at 6 weeks. Assuming that this expected non-progression rate at 6 weeks is equal to 61%, the 95% CI is [51%-71%] and the study will be stopped prematurely if ≥ 49 progressions (or deaths for progression) out of 100 evaluable patients for efficacy will be observed.

To be evaluable a patient must satisfy the following conditions:

- Patients must have received a minimum of one study treatment administration and have tumour assessment at baseline and during study (after week 6) unless progression or death from progression is documented before the first on-study tumour assessment at week 6. In this case, the patient will be considered as evaluable with early progression,
- In patients with measurable disease, all baseline target lesions must have been assessed at least once 6 weeks after randomisation, with the same method of measurement as baseline,
- In patients with only non-measurable disease, non-target lesions must have been assessed at least once 6 weeks after randomisation, with the same method of measurement as baseline.

No formal early stopping rule on safety criteria will be applied. However, given the toxicity associated with IV vinflunine and methotrexate a special attention will be paid to the rates of :

- febrile neutropenia
- neutropenic infection
- grade 3-4 ileus
- and toxic deaths

The results of the interim analysis will be submitted to IDMC for their recommendation to pursue or stop accrual in the study.

Tumour responses will be collected as soon as patients have been evaluated by the investigators. Adverse events reporting will be also closely monitored. Because the projected patient accrual could be slow in the study, the patient enrolment will continue while waiting the decision of the IDMC.

Following this interim analysis, a futility analysis has been carried out.

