### **5.1.1. Adverse Events Of Special Interest**

Adverse Events Of Special Interest (AEOSI) will be presented to facilitate monitoring of the following MedDRA preferred terms or Highest Level Terms of special interest: Myelosuppression, Febrile Neutropenia, Infections with severe neutropenia: clinically relevant Infections (potential bacterial origin), Constipation, Ileus, Intestinal obstruction, Abdominal pain, Nausea, Vomiting, Stomatitis / Mucositis, Diarrhoea, Myocardial infarction/ Ischemia, Cardiac arrhythmias, Cardiac conduction disorders, Local injection/infusion site reactions, Extravasation, Peripheral sensory neuropathy, Peripheral motor neuropathy, Autonomic neuropathy, Asthenia/fatigue, Myalgia, Immediate hypersensitivity, SIADH, PRES, Hepatic dysfunction,.

AEOSI will be programmatically determined from a predefined list presented in appendix 3.

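### SAP Appendix 3, item 2,2: a closed term list and a strict blood-count window can leave cases out of the grade 3 or worse rows for infections with severe neutropenia

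*SAP*

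**What the plan says.** SAP 5.1.1 names the category as infections with severe neutropenia, described as clinically relevant and of potential bacterial origin. It fixes the method: "AEOSI will be programmatically determined from a predefined list presented in appendix 3".

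Appendix 3, item 2,2 then gives the rule. On timing it says: "Time window is defined as 2 days before through 1 day after the onset of an infection". A blood-count condition must be met inside that period: "during which time grade 3 or 4 neutropenia or grade 4 leukopenia coincides". Below it stand 33 preferred terms, beginning with *neutropenic infection* and *neutropenic sepsis*. Airway entries include "bronchitis bacterial", *sinusitis*, "sinusitis bacterial", three pneumonia terms, *lung infection* and two lower respiratory tract terms. No minimum grade is set for the infection.

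SAP 11.2.2 presents each special-interest event by worst CTCAE grade per patient, and the list of tables in Appendix 1 confirms this.

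The protocol describes neutropenic infection in its dose-modification tables (Table 6 in 5.2.2.2, Table 11 in 5.2.3.2, Table 16 in 5.2.4.2) as grade 3 or higher "neutropenia concomitant with grade" 3 or higher infection. These tables have no term list, leukopenia route or day window. Protocol 11.5.6.2 says that "special attention will be paid to the rates of" four events: febrile neutropenia, neutropenic infection, grade 3-4 ileus and toxic deaths. It does not define neutropenic infection.

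**The concern.** A closed list counts only what it names. This population has head and neck cancer, and the protocol treats airway infection as relevant to safety. Exclusion criterion 6 bars patients with "Recurrent pulmonary or upper airways infections (3 times or more in the last 3 months) requiring antibiotics". Protocol 1.2.1.4 reports that the phase I study adopted a similar restriction after dose-limiting toxicities that included a grade 3 neutropenic infection. An infection coded to an unlisted airway term cannot enter the category, even if it is severe and the patient is neutropenic.

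The window raises a second problem. An event that the investigator reports as neutropenic infection or neutropenic sepsis already states the conjunction of interest. As written, it still needs a qualifying count within four days around onset.

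At stake is whether the final report describes a harm that the protocol singles out for attention. The primary survival analysis is not affected.

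**Working it through.** The plan states no rate for this event, so there is no figure to reproduce. The check has four steps.

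**1. Contents of the list.** A keyword search of the 33 terms gave:

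| Search | Terms found |
|---|---|
| bronch- | 1 (*bronchitis bacterial*) |
| sinus | 2 (*sinusitis*, *sinusitis bacterial*) |
| respiratory | 2 (both lower respiratory tract) |
| pneumon- | 3 (*pneumonia*, *pneumonia bacterial*, *lobar pneumonia*) |
| aspir-, upper, pharyng-, laryng-, trache-, tonsil- | 0 each |

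**2. The two definitions side by side.**

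| Element | SAP item 2,2 | Protocol Tables 6, 11, 16 | Effect on the SAP count |
|---|---|---|---|
| Infection terms | 33 listed | Any | Lowers |
| Timing | Day -2 to +1 of onset | Concomitant, not defined further | Lowers where no qualifying count falls in the window |
| Infection grade | No minimum | 3 or higher | Raises the any-grade row only |
| Blood count | Neutropenia grade 3-4 or leukopenia grade 4 | Neutropenia grade 3 or higher | Raises very little |

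The last line follows from SAP 15.2.4.1. Grade 4 leukopenia is a white cell count below 1, and a neutrophil count below 1 is already grade 3 or worse. Neutrophils are part of the white cells, so a white count below 1 implies a neutrophil count below 1. The leukopenia route therefore adds cases essentially only when the neutrophil count is missing.

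**3. Direction.** Let N be the number of patients having an infection with severe neutropenia. Let g be the share whose infection is grade 3 or higher, and u the share that the SAP misses through list or window. Assume that u does not depend on grade, and ignore the leukopenia route. Neither g nor u is in the documents.

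- Protocol count = g × N.
- SAP grade 3 or worse rows = (1 - u) × g × N. The ratio to the protocol count is 1 - u, which cannot exceed 1.
- SAP any-grade row = (1 - u) × N. The ratio is (1 - u)/g, which is below 1 only if u > 1 - g.

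| g | Ratio for any grade, u = 0.1 | Ratio for any grade, u = 0.5 | Break-even u |
|---|---|---|---|
| 0.3 | 3.0 | 1.67 | 0.70 |
| 0.5 | 1.8 | 1.0 | 0.50 |
| 0.7 | 1.29 | 0.71 | 0.30 |
| 0.9 | 1.0 | 0.56 | 0.10 |

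Over the same range of u, the grade 3 or worse rows hold 1 - 0.1 = 0.9 down to 1 - 0.5 = 0.5 of the protocol count.

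**4. How the window meets the count schedule.** The protocol flow chart schedules counts on days 1 and 8 in arm A and on days 1, 8 and 15 in arm B. One count covers four possible onset days, from the day before it to two days after it. With 21-day cycles and onset uniform over the cycle (assumption), scheduled counts alone cover 2 × 4/21 = 8/21 = 38% of onset days in arm A and 3 × 4/21 = 12/21 = 57% in arm B. Unscheduled counts raise both figures by an unknown amount.

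**The case against.** The strongest reply is that the list is broad and the category is not meant to be the protocol's event. Pulmonary infection is well represented, and generic entries such as *infection* and *bacterial infection* catch loosely coded reports. The wording with grade 3 infection appears only in dose-modification tables. The SAP category has its own name and scope, and the interim analysis for which the protocol asked for attention has already taken place. This stands: the SAP does not promise to estimate the dose-modification event. It is still the only planned table linking infections to severe neutropenia, and nothing explains why its rule differs.

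The second reply is that unlisted infections are still reported. SAP 11.2.1 and 11.2.3 tabulate all treatment-emergent and serious events by organ class and preferred term, and individual listings of events and blood counts are planned. This is true, but the tables do not link an infection to a count, so recovering the rate would mean working through listings by hand. The adjacent febrile neutropenia item does not fill the gap, because SAP 5.2 restricts it to fever without documented infection.

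Four stronger readings are tempting, and the documents do not support them.

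- *The rate is undercounted overall.* A reader might infer this from the missing terms. The any-grade row has no minimum infection grade and can exceed the protocol count.
- *The loss is larger in arm A.* The 38% and 57% in the working suggest it. However, protocol 5.2.2.2, in the vinflunine section, asks for an immediate count at fever or infection, whereas Table 19 in 7.4 leaves it to institutional standards and the investigator. Capture could be better in arm A.
- *Airway infection is the main infection risk here.* Exclusion criterion 6 shows that it matters, but no passage ranks the risks.
- *The loss is 1 to 4 percentage points.* This comes from assuming that 10% of 230 arm A patients (23) have the event and that 10-40% of them carry unlisted terms, which gives 2.3 to 9.2 patients. Neither input is in the documents, and the safety table counts treated, not randomised, patients.

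**Conclusion.** The point holds in a limited form. The list has no aspiration, unspecified bronchitis, general respiratory or upper respiratory, pharyngeal, laryngeal or tracheal term. The window, read literally, removes reported neutropenic infections and neutropenic sepsis that lack a qualifying count. Compared with protocol Tables 6, 11 and 16, the grade 3 or worse rows can miss cases and have almost no route by which to gain them. The any-grade row may be higher or lower.

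The size of the loss and any difference between arms cannot be determined from the documents. The ratios in the working show direction only. They rest on assumed g and u, and on u being unrelated to infection grade. This is a descriptive safety table, so the point is a cheap improvement and does not threaten the trial's conclusion on survival.

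**What to change.** Amend Appendix 3, item 2,2 in three ways.

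1. Add the missing airway and aspiration terms, or replace the list with a MedDRA grouping. Appendix 3 already uses High Level Terms for arrhythmias, conduction disorders and injection-site reactions.
2. Count *neutropenic infection* and *neutropenic sepsis* as reported, without requiring a blood count in the window.
3. Add one row for infection of grade 3 or higher with neutropenia of grade 3 or higher, and state there what counts as concomitant, since the protocol tables do not say.

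A footnote should say how the category relates to Tables 6, 11 and 16. The cost is an Appendix 3 edit and slightly more programming on data already collected. The downside is that a few minor infections will enter the any-grade row.

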
End of study
 
The end of study is the date of the last patient study treatment administration plus 30 days.
 
No follow-up visit will be performed. At the time of the amendment PA11:
 
 - Patients under treatment will stop the study at the EOT. - Patients under follow-up will stop immediately. 	

Study L00070 IN 309 F0
	

Table 1: Study flow chart

Required assessments	Screening period	Treatment period		End of treatment (f)	Follow-up (g)
	Day - 21 to - 1	Day 1 every cycle	Every 6 weeks		
Signed informed consent	X (a)				
Demographic data					
Demography/Medical History/Diagnosis	X				
Serum or urine pregnancy test in women of childbearing potential	X (j)				
Physical Examination/Vital signs/Weight	X (b)	X		X	
WHO Performance Status	X (b)	X		X	X
Safety					
Electrocardiogram (ECG)	X (m)	X (m)			
Pre-treatment events/Adverse events/SAE	X (k)	X		X	X
Complete blood cell count (l)	X (b)	X (c) (within 24 hours)		X	
Blood chemistry (d)	X (b) (e)	X	X (e)	X (e)	
Concomitant medications/Blood Products	X(k)	X		X	
Efficacy (i)					
Cervical CT-Scan or MRI	X		X	X	X (h)
Chest/upper abdominal CT-Scan or MRI	X		X	X	X (h)
Other imaging if necessary	X		X	X	X (h)
Health-related quality of life					
EORTC QLQ-C30 and QLQ-H & N 35	Before randomisation within 24h		X	X	

(a) Prior to any study procedure.

(b) Within 7 days prior to first study drug treatment.

(c) CBCC performed on days 1 and 8 in arm A; on days 1, 8 and 15 in arm B

(d) Transaminases, alkaline phosphatase, total bilirubin, urea, creatinine, calculated (Cockcroft-Gault) creatinine clearance, calcium, sodium, potassium, magnesium, chloride, bicarbonate.

(e) Glucose, total protein and albumin to be performed in addition.

(f) Within 30 days after study treatment discontinuation.

(g) Until disease progression: every 6 weeks. After disease progression, every month for the first 6 months and then every 3 months until death.

At the time of the amendment PA11, no more follow-up visit will be performed.

(h) In case of treatment discontinuation for other reason than PD, all efficacy assessments must be performed every 6 weeks from time of randomisation until disease progression is documented, then survival information will be collected approximately every month for the first 6 months then every 3 months until death.

At the time of the amendment PA11, these assessments will not be performed.

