5.1.2. Methotrexate (arm B)

Descriptions of study drug, storage, packaging, labelling and drug accountability are given in section 10.

Patients randomised to arm B will receive methotrexate on a weekly basis as a bolus intravenous injection at the dose of 40 mg/m²/week. The drug will be administered by direct injection through the side arm of a freely running NS or 5% glucose solution IV infusion.

One cycle of methotrexate is defined as a three-week period, i.e. 3 weekly administrations of methotrexate (days 1, 8, and 15).

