### **Patients will be randomised to receive:**

- Arm A : i.v. vinflunine 280 mg/m^2 on day 1 and methotrexate 30 mg/m^2 on days 1 and 8 every 3 weeks.
- Arm B : methotrexate 40 mg/m^2/week.

Overall survival (OS) will be the primary endpoint of the study. The final analysis will require at least 437 deaths. The study has been powered at 90% to show an improvement of survival from 5.5 months in the control arm to 7.5 months in the test arm.

Throughout the study, patients will be closely monitored for safety evaluation and will be assessed for tumour response every 6 weeks. Patients will receive at least 2 cycles unless they experienced unacceptable toxicity or early disease progression. Patients who respond or have stable disease will

receive 2 additional cycles and will be reevaluated for tumour response. Patients with progressive disease will be removed while patients who respond or have stable disease may continue study treatment until disease progression.

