### **11.2.2. Selected adverse events**

The worst CTCAE grade per patient of Adverse Events Of Special Interest (AEOSI) listed in section 5.1. will be presented for patients treated in both arms and regarding the relationship to treatment.

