## 11.3. LABORATORY TESTS

### 11.3.1. Haematological toxicities

Leukocytes, ANC, haemoglobin and platelets data will be analysed for haematological toxicity.

A first analysis will present the worst grade by patient and the worst grade experienced during a cycle. Cycles where a grade 3/4 haematological toxicity occurred will be listed by patient number. In a second analysis, the worst grade of patients according to the grade at baseline will be tabulated.

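### The immediate-hypersensitivity event of special interest is timed to day 1 and vinflunine but tabulated for both arms, so it misses two of three arm B dosing days; sparser scheduled blood counts in arm A need a footnote

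*SAP*

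**What the plan says.** **Hypersensitivity.** SAP Appendix 3, item 9, requires that a listed term be related to study drug and that it "occur on the day of study drug infusion (day 1 or within 24 hours after infusion of vinflunine". SAP 5.1.1 has events of special interest picked out by program from that appendix. SAP 11.2.2 says that their worst grade per patient "will be presented for patients treated in both arms and regarding the relationship to treatment".

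**Dosing.** In arm A, vinflunine and methotrexate are given on day 1 and methotrexate alone on day 8 (SAP section 2). For arm B, Protocol 5.1.2 states: "Patients randomised to arm B will receive methotrexate on a weekly basis as a bolus intravenous injection". It fixes the cycle length ("One cycle of methotrexate is defined as a three-week period") and the dosing days: "3 weekly administrations of methotrexate (days 1, 8, and 15".

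**Blood counts.** Protocol Table 1, footnote (c), gives the schedule: "CBCC performed on days 1 and 8 in arm A; on days 1, 8 and 15 in arm B". SAP 11.3.1 sets the summary: "A first analysis will present the worst grade by patient and the worst grade experienced during a cycle". Under SAP 5.3 a cycle is evaluable in either arm if it has one count from day 2 up to day 1 of the next cycle.

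**The concern.** A safety row shown side by side for two arms should give each arm the same chance of an event being counted at each dose. Item 9 appears to have been written around vinflunine. It names day 1 and the 24 hours after a vinflunine infusion, and gives no window for methotrexate on days 8 or 15. Because a program applies the rule, the wording decides what is counted.

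The blood-count issue is of another kind and points the other way. The period searched is the same in both arms, but arm A has fewer scheduled looks inside it. A worst grade is a maximum over the available counts, so fewer looks tend to give a lower maximum. The special-interest event of myelosuppression (Appendix 3, item 1) is graded from the same laboratory values, so it inherits the difference.

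Safety was kept in full when the efficacy analyses were cut back (Protocol 11.5.1, SAP section 13), so these tables will carry much of the report's comparison of the regimens.

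**Working it through.** The plan states no figure on this point, so the check compares schedules.

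**1. Hypersensitivity: which dosing days qualify under item 9 as written**

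| Arm | Dosing day | Drug | Covered? |
|---|---|---|---|
| A | 1 | vinflunine + methotrexate | yes, with the 24-hour extension |
| A | 8 | methotrexate | no |
| B | 1 | methotrexate | yes, without the extension (no vinflunine) |
| B | 8 | methotrexate | no |
| B | 15 | methotrexate | no |

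Days left out: 1 of 2 in arm A, 2 of 3 in arm B. The arm A omission concerns methotrexate only, since every vinflunine dose is covered. Arm A patients who stop vinflunine and continue on methotrexate alone (Protocol 5.2.5, SAP 9.2.9) also lose the vinflunine anchor.

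*Illustration.* Assume that each arm B dose carries the same independent risk q of a same-day reaction, over c cycles. The share of arm B patients with a reaction who enter the row is [1 − (1 − q)^c] / [1 − (1 − q)^(3c)]:

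- q = 0.5%, c = 1: 0.0050 / 0.0149 = about 34%
- q = 1%, c = 2: 0.0199 / 0.0585 = 34%
- q = 2%, c = 4: 0.0776 / 0.2153 = 36%

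The share stays close to one third. The number of events missed depends on q, which the documents do not give.

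**2. Blood counts: scheduled counts within the SAP 5.3 window (day 2 to next day 1, taken as day 22)**

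- Arm A: days 8 and 22. Two counts; longest gap 22 − 8 = 14 days.
- Arm B: days 8, 15 and 22. Three counts; longest gap 7 days.

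Three provisions add counts. In arm A, a low day 8 count delays the dose to day 15 with a reassessment (Protocol 5.2.3.2, Table 10). Fever or infection prompts a count (Protocol 5.2.2.2, Table 19). Clinically significant abnormal results are repeated until normal or stable (Protocol 9.1.1). SAP 5.3 and 11.3.1 do not exclude such counts. The gap that remains is mainly an afebrile fall in arm A after an acceptable day 8 count.

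*Can the effect be sized?* Two simple models, both ignoring triggered counts and both assuming identical toxicity in the two arms:

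- Each count has an equal, independent chance p of showing the grade. Detection per cycle is 1 − (1 − p)² in arm A and 1 − (1 − p)³ in arm B. p = 5%: 9.8% v 14.3% (ratio 1.46). p = 30%: 51.0% v 65.7% (ratio 1.29).
- One low-count episode of L days, with onset uniform over days 2 to 21. L = 3: 25% v 40% seen (ratio 1.60). L = 5: 45% v 70% (1.56). L = 7: 65% v 100% (1.54). L = 14: 100% v 100% (1.00).

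The ratio runs from 1.0 to 1.6 depending on assumptions about the timing, duration and frequency of low counts, none of which the documents settle.

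**The case against.** **On hypersensitivity.** The leading phrase of item 9 refers to the day of study-drug infusion, and the parenthesis could be taken as a gloss rather than a limit. On that reading every dosing day might count. But the parenthesis names only day 1 and vinflunine, and methotrexate is a bolus injection, so a programmer following the text would not reach days 8 and 15 in arm B. At best the rule is ambiguous where it has to be exact.

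A reader might infer that these reactions vanish from the safety report. The documents do not support that. Treatment-emergent events are tabulated by system organ class and preferred term whatever their timing (SAP 11.2.1; Appendix 1, per patient and per cycle), and adverse events are listed individually. Only the special-interest row is short. The protocol's list of expected methotrexate effects (1.1.1) names a transient rash but not hypersensitivity, so the number affected may be small. The omission also favours the control arm, so it does not flatter the test regimen.

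**On blood counts.** The sampling follows the dosing, with a count at each dosing day in each arm, and the evaluability window is common to both. The tables are descriptive and no test is planned. The triggered counts narrow the difference. All of this stands.

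A reader might also infer from two looks against three that arm B would show severe grades 1.4 to 1.5 times as often at equal toxicity. That figure needs independent counts with one small, constant probability. Counts within a cycle are unlikely to be independent, and vinflunine is given on day 1 only, so a constant risk across days 8, 15 and 22 is doubtful. The documents do not support a figure.

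**Conclusion.** The hypersensitivity point holds. As written, item 9 leaves out 2 of 3 arm B dosing days and the arm A day 8 methotrexate dose, while its result is shown for both arms. The row therefore under-captures events mainly in the control arm. This rests on reading the parenthesis as the operative window. The effect on reported incidence is unknown, because no hypersensitivity rate is given, and it is confined to one row of descriptive output. Type I error is not affected.

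The blood-count point holds only as a caveat. Scheduled sampling after day 1 is two counts per cycle in arm A and three in arm B, so some asymptomatic falls in arm A between day 8 and the next cycle may go unseen. The direction is plausible, but the size cannot be derived from the documents.

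**What to change.** **Appendix 3, item 9.** Define immediate hypersensitivity as a listed event, related to study drug, with onset on the day of, or within 24 hours after, any administration of vinflunine or methotrexate (days 1, 8 and 15 as applicable), in either arm. The cost is one changed definition and its program, using administration and onset data already collected.

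**SAP 11.3.1 and Appendix 3, item 1.** Keep the all-counts worst-grade tables as the main presentation. Add a footnote that scheduled counts are sparser in arm A (days 1 and 8) than in arm B (days 1, 8 and 15), so asymptomatic falls after an acceptable day 8 count may be missed in arm A. This costs a sentence.

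A table restricted to the days that both arms share (day 8 and next day 1) may be added as a supplementary display only. It should not become the basis for comparing the arms. It would discard arm B's day 15 counts and also arm A's day 15 rechecks and fever- or infection-triggered counts, where severe neutropenia is likely to appear, and it cannot recover lows in arm A that were never sampled.

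Neither change alters treatment, visits or data collection.
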